### **6.2.12 Randomization Strata**

The randomization will be stratified by biopsy class (Class V only versus Others) and by prior MMF use at time of screening. A regional blocking factor will also be used for supply purposes ensuring balance within region. The stratification factors and the regional blocking factor will be used as covariates in the primary analyses.

Tables of events or medications will be ordered in descending frequency of subjects followed by (where applicable) events for the higher level term (system organ class or ATC levels 4 and 2) followed by the preferred term. Ordering will be for the VCS treatment group first followed by the placebo group and alphabetical thereafter.

Listings will be sorted in the following order treatment group, subject, parameter, and visit unless otherwise stated. All data will be listed, subjects who were not randomized will be displayed after the randomized treatment groups.

Continuous variables will be summarized by the number of non-missing observations, mean, median, standard deviation, and minimum and maximum. For all tabulations of changes from baseline data, the lower and upper 95% confidence limits for the mean for the individual treatments will be given.

Categorical variables will be summarized by presenting the frequency and percent. Percentages will be based on the number of non-missing observations out of the subject population unless otherwise specified. For each variable, all categories will be shown. Zero frequencies (but not the percent) within a category will be presented.

### **6.3.1 Decimal Places**

Derived data where it is known in advance the result will be an integer for example day, month, year, number of days and total scores (for rating scales) will be presented with zero decimal places.

Means, medians and percentiles will be displayed to one more decimal place than the data, dispersion statistics (e.g., standard deviation) will have two more decimal places, and the minimum and maximum will be displayed to the same number of decimal places as reported in the raw data. Percentages will be displayed with one decimal place.

P-Values will be quoted to 3 decimal places. P-values < 0.001 will be presented as p<0.001.

## **6.4 Subject Disposition**

Subject disposition will be summarized as follows:

- The number of subjects who entered the study, were randomized and who are in each analysis population will be summarized by treatment group and overall for the ITT population. This summary will be repeated for individual levels of the stratification and blocking variables. The reasons for exclusion from the Per-Protocol population will be summarized by treatment group and overall.

- The number of subjects who failed screening and the reasons for failure will be tabulated for all subjects. The number of subjects that were screened once, twice, 3 times, and total number of screened subjects will also be summarized.
- The number of early withdrawals and the reasons for withdrawals will be tabulated by treatment group and overall for the ITT population.
- The number of subjects that discontinue study drug will be presented by treatment group and visit for the ITT population.
- The number of subjects who complete Week 24, and those who complete Week 52 will be summarized for the ITT population.
- A summary of study drug discontinuation will be provided by visit for the ITT population.

## **6.5 Protocol Deviations**

Major protocol deviations will be grouped into categories and summarized by treatment group and overall for the Safety and ITT populations. A listing of protocol deviations will be provided.

## **6.6 Baseline Comparability**

The comparability of treatment groups with respect to subject demographics and baseline characteristics will be assessed in a descriptive manner, but no formal statistical testing will be performed.

Standard continuous or categorical variable summaries will be presented for the following variables based on the SS. Demography and disease history will also be summarized for the ITT and safety populations.

- Demographic data (summarized additionally by country and region for the Safety population)
- Disease history (including eGFR and UPCR measures)
- Medical/Surgical/ Systemic Lupus Erythematosus /Renal history
- Physical examination by body system at screening.

Regions and countries within regions are as follows:

Region	Country
Asia Pacific	Japan Korea (the Republic of) Malaysia Philippines (the) Thailand Taiwan (Province of China) Viet Nam
Europe + South Africa	Bulgaria Belarus Spain Croatia North Macedonia Netherlands (the) Poland Russian Federation (the) Serbia Turkey Ukraine South Africa
Latin America	Argentina Brazil Chile Colombia Costa Rica Dominican Republic (the) Guatemala Mexico Peru
North America	Canada United States of America (the)

## 6.7 Medical History

The results of the kidney biopsy will be summarized. Separate tabulations of previous and ongoing medical conditions, history of systemic lupus erythematosus (SLE) related conditions, and Renal (lupus nephritis) history collected at screening will be presented by treatment group and overall for the ITT and Safety. Conditions will be presented by Medical Dictionary of Regulatory Activities (MedDRA) primary system organ class and preferred term.

The summary of Lupus History summary for SLE involvement will include the following categories:

- Mucocutaneous

- Neurological
- Musculoskeletal
- Cardiorespiratory
- Vasculitis
- Hematology
- Antiphospholipid Syndrome
- Any other current SLE involvement to record (If 'Yes' it will be recorded)

For each of these categories, the following items will be summarized: Ever Involved (Yes/No), Currently Involved (Yes/No), years since onset.

The summary of the history of SLE related conditions will include the following categories:

- Diabetes Mellitus
- Hypertension
- Myocardial Infarction
- Stroke
- Deep Vein Thrombosis
- Hyperlipidemia

For each of these categories, both ever diagnosed and SLE related will be summarized.

Details of specific conditions falling into these categories will also appear in the General Medical History summary and treatments in the prior and/or concomitant medication summaries.

The number of years prior to baseline since diagnosis of the first occurrence of SLE will be summarized. For Renal History, the number of years prior to baseline since the 1st instance of a significant proteinuria (>500 mg/day), and the number of years prior to baseline since the first diagnosis of LN will be summarized as a continuous variable. Any previous dialysis (Yes/No),

and the number of years prior to baseline since the last dialysis will also be summarized. ‘Years since...’ variables will be calculated as year of informed consent – year of event + 1.

All data will be listed and a glossary of unique verbatim terms with coding information will be provided.

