### **9.2.1 Screening Visit Procedures**

The screening visit (Visit 1) will take place within 30 days prior to Visit 2/baseline (Day 1). Screening will include provision of informed consent, physical examination including weight, and height, medical history (including SLE and LN history), vital signs measurements, 12-lead ECG, and review of prior and concomitant medications and entry criteria. Any AEs which occur after informed consent will be recorded. Urine samples will be collected for urinalysis and urine microscopy; first morning void urine samples (for determination of UPCR) will be collected on 2 days during the screening period and must be returned and the results evaluated prior to Visit 2. An average of the 2 screening UPCRs will be used as a marker of baseline urine protein excretion. Baseline proteinuria level is determined by a mean of 2 first morning void urine samples taken during the screening period. The lowest of pre-dose eGFR assessments will be used as the marker of baseline renal function. It is recommended that in the event that IV corticosteroids are administered during screening, the 2 first morning urine voids are to be collected prior to administration of the corticosteroids (see Section 7.2.2.2, [Corticosteroids](#)). In the case where this is not possible, then the marker of baseline urine protein excretion will be based upon the Visit 1 UPCR collection only. This must be discussed with the Medical Monitor prior to enrollment. Please note that the results of the 24-hour urine collection will have to be available prior to the Baseline Visit.

Blood samples will be drawn according to [Table 2](#).

If the subject is from an area where TB is endemic or whose history suggests an increased personal risk, e.g., from contact with people with TB or travel to areas with endemic TB, the subject will be carefully evaluated for latent or active TB.

Women of childbearing potential should have a negative serum pregnancy test result before randomization. Study treatment cannot be initiated by the physician until a report of a serum negative pregnancy test has been obtained.

If a subject has not met the requirements in Inclusion Criteria #4 due to not having kidney biopsy result within the required time frame, a kidney biopsy can be performed as per local procedures, after signing the study consent, provided the results can be obtained and reviewed prior to randomization.

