### **14.1 Informed Consent**

The ICF used for the study must comply with the Declaration of Helsinki, federal regulations, and ICH guidelines; and must have been approved by the Institutional Review Board (IRB)/Ethics Committee (EC)/Independent Ethics Committee (IEC) prior to use. The Investigator or an authorized associate must explain the nature of the study and the treatment in such a manner that the subject is aware of potential benefits and risks. Subjects must also be informed that participation is voluntary and that they may withdraw from the study at any time, without prejudice. Subjects must be provided sufficient time to consider participation, including discussion with family members prior to signing the ICF. Documentation of the discussion and the date of informed consent must be recorded in the source documentation. After signing the ICF, subjects will be enrolled into the study and assigned a subject identification number that will be used on all subject documentation.

The informed consent can be signed up to 30 days before the screening Visit 1. If more than 30 days elapses between date of consent and the screening Visit 1, the subject should be asked to re-sign and date the consent form to confirm continued interest in study participation.

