### **6.2.8 Missing Diagnosis Dates**

If the month and year are present but the day is missing, the diagnosis date will be set to first day of the relevant month. If only the year is recorded the diagnosis date will be set as "01-Jan" for that year.

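### The 'years since' formula in SAP 6.7 adds 1 to a calendar-year difference and so overstates reported disease durations by about one year on average

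*SAP*

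**What the plan says.** SAP 6.7 Medical History describes the target as elapsed time before baseline. For SLE: "The number of years prior to baseline since diagnosis of the first occurrence of SLE will be summarized". For renal history it lists time since first significant proteinuria, time "since the first diagnosis of LN will be summarized as a continuous variable", and time since last dialysis. For each category of SLE involvement it also asks for years since onset.

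The same section gives one rule for all of these: each "will be calculated as year of informed consent" less the year of the event, plus 1 (in full, "variables will be calculated as year of informed consent – year of event + 1"). It gives no reason for the added 1 and does not label the result an inclusive count of calendar years. The SAP amendment table shows that this calculation was updated in version 5.0, so the formula is the operative one.

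SAP 6.2.8 Missing Diagnosis Dates completes partial diagnosis dates to a full date. If only the day is missing, "the diagnosis date will be set to first day of the relevant month"; if only the year is known, 1 January is used. The formula in 6.7 uses neither day nor month.

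**The concern.** The quantity described and the quantity computed are not the same. The text promises years before baseline. The formula counts calendar years touched between event and consent, including both end years. A subject diagnosed two weeks before consent is reported as having at least 1 year of disease, and as 2 years if New Year falls in between.

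What is at stake is the description of the enrolled population. Time since SLE and LN diagnosis tells a reader how early or late in their disease the subjects were. A shift of about a year matters little against a long history but is large in relative terms for recent diagnoses. These can occur here, because inclusion criterion 4 allows the qualifying biopsy to be done during screening.

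**Working it through.** The documents give no numerical result for these variables, so there is no figure to reproduce. The check is on the formula.

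**Inputs**
- Formula: SAP 6.7, as quoted.
- Target: years prior to baseline, SAP 6.7.
- Consent to screening: "The informed consent can be signed up to 30 days before the screening Visit 1" (Protocol 14.1). Screening is at most 30 days before baseline (Protocol 9.2.1). Consent to baseline is therefore 0 to about 60 days, or 0 to 60/365.25 = 0.16 year.
- Distribution of true durations: not in the documents. Four were assumed.

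**Algebra.** Write consent as Yc + u and the event as Ye + v, where u and v are the elapsed fractions of their calendar years (0 ≤ u, v < 1).
- True elapsed time at consent: D = (Yc − Ye) + u − v
- SAP value: (Yc − Ye) + 1
- Error = SAP value − D = 1 − u + v

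Since u and v are each at least 0 and below 1, the error is always above 0 and below 2 years.

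**Mean error.** The year difference counts the New Years crossed. If consent dates are evenly spread over the year, an interval of length D crosses D New Years on average, so E[Yc − Ye] = D. The plain difference is unbiased and the mean error of the SAP rule is exactly 1.

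**Simulation** (1,000,000 draws per setting, evenly spread consents, measured at consent):

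| Assumed true duration | True mean (years) | Mean under SAP rule | Mean error |
|---|---|---|---|
| Uniform 0 to 0.5 | 0.25 | 1.25 | 1.00 |
| Uniform 0 to 2 | 1.00 | 2.00 | 1.00 |
| Exponential, mean 5 | 5.01 | 6.01 | 1.00 |
| Exponential, mean 7 | 7.01 | 8.01 | 1.00 |

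**Sensitivity to consent timing.** Mean error = 1 − E[u] + E[v], taking E[v] = 0.5.
- All consents in the first half of the year: 1 − 0.25 + 0.5 = 1.25
- All in the second half: 1 − 0.75 + 0.5 = 0.75

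The simulation gave the same two values under all four distributions.

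**Measured to baseline,** with evenly spread consents and a fixed lag:
- 30 days: 1 − 30/365.25 = 0.92 year
- 60 days: 1 − 60/365.25 = 0.84 year

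At these lags, at most about 1.3% of subjects are slightly understated.

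**Single cases, measured at consent**

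| Event | Consent | True years | SAP value |
|---|---|---|---|
| 31 Dec 2017 | 1 Jan 2018 | 0.003 | 2 |
| 1 Jun 2018 | 15 Jun 2018 | 0.04 | 1 |
| 1 Jul 2012 | 1 Jul 2018 | 6.0 | 7 |
| 1 Jan 2018 | 31 Dec 2018 | 0.997 | 1 |

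**After removing the added 1:** the mean error at consent is 0.00 with evenly spread consents, and individual errors lie between −1 and +1 year.

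**The case against.** The best defence is that this is a stated convention and not a slip. The calculation was revised after review, and a year-based rule is workable when some event dates are known only to the year, as 6.2.8 expects. The SAP also counts inclusively elsewhere: study day in 6.2.4 adds 1. The variables are descriptive. SAP 6.6 rules out formal testing of baseline comparability, and disease duration is absent from the primary logistic model, the listed sensitivity factors, the Cox model and the repeated-measures model.

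The point about consequence stands in full. The convention argument only partly stands. Working in whole years is defensible, but that does not call for the added 1, since the plain difference is unbiased for year-only data too. In 6.2.4 the inclusive count costs one day; here it costs a year. An inclusive count would also need to be labelled as one, and 6.7 instead says years prior to baseline.

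A reader might infer more than the documents support:
- *That newly diagnosed subjects are hidden.* They are not. Every event in the consent year gets the minimum value of 1; without the added 1 the same group would get 0. The lost resolution comes from using whole years, and 6.7 also provides for listing all data.
- *That every duration is wrong by exactly one year.* One year is an average that depends on consent timing; individual errors vary widely.
- *That 6.2.8 contradicts 6.7.* It does not. The completed dates are simply not needed by a year-only rule.
- *That all these durations are specified as continuous variables.* 6.7 uses that term only for proteinuria and LN.

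**Conclusion.** The point holds as a small, real error of derivation. Followed as written, SAP 6.7 overstates the reported durations by about 1 year on average. The figure of 1.00 rests on consent dates being evenly spread over the calendar year. The range of 0.75 to 1.25 brackets the case where all consents fall in one half of the year and events average mid-year. The values of 0.84 and 0.92 to baseline rest on fixed 60- and 30-day lags; actual lags are not in the documents.

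It would be wrong to read this as a threat to the trial's conclusions. The shift is expected to be the same in both arms, and no efficacy model, alpha allocation or power calculation uses these variables. It affects only the description of the population.

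**What to change.** Delete the added 1 in SAP 6.7. That alone removes the systematic shift at consent when consent dates are evenly spread.

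Preferably, where at least month and year of the event are recorded, use (baseline date − event date)/365.25. This also matches the section's reference to baseline. With a missing day, the first-of-month rule in 6.2.8 leaves only about half a month (0.5/12 = 0.04 year).

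For year-only dates, use the plain calendar-year difference and not the 1 January imputation. Exact subtraction from 1 January would overstate duration by about 0.5 year on average if events are spread over the year. Because 6.2.8 addresses diagnosis dates only, the sentence should also say how partial dates are handled for first proteinuria, last dialysis and onset of SLE involvement.

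If the sponsor wants to keep the present formula, the minimum is to label the output an inclusive count of calendar years at consent.

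The minimal change costs one SAP sentence and one line of derivation code; the preferred version adds the partial-date rule. No new data are needed.

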## 6.8 Prior and Concomitant Medications

Separate tabulations will be produced for prior and concomitant medications presented by treatment group and overall for the Safety population. Prior medications are defined as all medications starting and stopping before the date of first dose of study drug. Concomitant medications are defined as medications taken on or after the date of first dose of study drug. Medications will be summarized using ATC Level 2, 4, and preferred term.

The following previous LN therapies will also be summarized: MMF, IVC, Corticosteroids, Methotrexate, CNI, Biologic, Azathioprine, Antimalarial, other. The responses for these LN therapies are Yes or No.

All medications will be listed and a glossary of unique verbatim terms with coding information will be provided.

## 6.9 Exposure to Study Drugs

Overall exposure to study drugs (number of days of exposure to study drugs and mean dose) will be presented for both the Safety and ITT populations. Exposure will be based on prescribed dose. Exposure will not be summarized by visit but for the overall study duration. Overall study drug exposure will be calculated from the first dose date to the last dose date plus 1 for each prescribing record. Care should be taken to not double-count days. It is expected that prescription records will cover each study day between randomization and the end of study (or early termination). Periods of zero dose will be assigned as such.

The following gives an example of a subject with 4 prescription records over the 52-week (365 day) period.

**Table 6.1 Exposure calculation example**

Start Day	End Day	Dose (bid)	Duration
1	180	3	180 days
181	200	0	20 days
201	230	2	30 days
231	365	3	135 days

For the purposes of analysis this subject will have ‘days on treatment’ calculated as 180+30+135 = 345 days. Their mean daily dose will be:

$(180*3 + 20*0 + 30*2 + 135*3) / 365 = 2.75$  caps BID (converted to 43.45 mg per day).

Gaps between dosing records will be counted as a zero dose. For IV methylprednisolone, gaps between doses will not be taken into consideration.

For subjects who are lost to follow-up, and for whom the last dose date from the termination record is unknown, the date of the last available visit will be used as the last dose date.

Exposure to study drug will be summarized for the following:

- VCS/placebo
- MMF
- IV methylprednisolone
- Corticosteroids

Prescribed dose changes (Yes/No) at visit intervals and overall will be summarized for VCS/Placebo and for MMF.

## 6.10 Treatment Compliance

All unused study treatments (and any empty containers) dispensed to the subject will be returned at each study visit for capsule counts to check compliance. The Investigator will count the returned study treatment and this information will be used to assess subject compliance. Each subject is expected to take 6 capsules a day (47.4 mg/day, 23.7 mg BID, 3 capsules BID) with each softgel capsule = 7.9 mg. It should be noted that compliance will not be summarized by visit but for the overall study period.

Subject compliance with study drug (VCS / placebo) will be summarized by treatment group. Counts of the returned study treatment will be used to assess subject compliance. The study treatment count will be documented in the eCRF and source documentation.

Subject compliance will be calculated as:

$$\text{Compliance (\%)} = \frac{\text{number of dispensed capsules} - \text{number of returned or lost capsules}}{\text{number of prescribed capsules}} \times 100$$

The number of prescribed doses will be calculated as per the exposure calculation.

Compliance with the protocolled steroid taper will also be assessed and summarized. Subjects will be assessed as being either compliant or non-compliant.

## 6.11 Efficacy Analyses

All statistical tests will be performed using a two-tailed 5% overall significance level, unless otherwise stated. All comparisons between treatments will be reported with 95% confidence intervals for the odds ratio, hazard ratio or difference as applicable.

### 6.11.1 Primary Endpoint

The primary endpoint is the number of subjects showing renal response at 52 weeks. Renal response at Week 52 will be adjudicated by the CEC based on the following parameters:

- UPCR of  $\leq 0.5$  mg/mg, and
- eGFR  $\geq 60$  mL/min/1.73 m^2 or no confirmed decrease from baseline in eGFR of  $>20\%$ , and
- Received no rescue medication for LN, and
- Did not receive more than 10 mg prednisone for  $\geq 3$  consecutive days or for  $\geq 7$  days in total during Weeks 44 through 52, just prior to the renal response assessment

The CEC will be blind to treatment group and completely independent of Aurinia. They will also take into consideration the following:

- Subjects who withdraw from the study prior to the Week 52 assessment and thus provide insufficient Week 52 data will be defined as non-responders
- Medication listings will be reviewed by the CEC as part of the adjudication process. The CEC will have complete autonomy to adjudicate any treatment as rescue medication. However, as any dose of MMF is permitted within this protocol there is no MMF dose level that necessarily classifies it as being rescue medication. As part of this review the CEC will also adjudicate on steroid drug use beyond the protocolled taper.

- eGFR values eliminating a subject from complete remission should be accompanied by a treatment or disease-related TEAE that impacts eGFR. To this end, eGFR measures which would ordinarily result in a subject not being in remission will only be used if the first eGFR assessment occurs on a date where there is also a treatment or disease-related, eGFR associated TEAE. The following is a list of MedDRA preferred terms that are associated with eGFR decreases:
  - BLOOD CREATININE INCREASED
  - CREATININE RENAL CLEARANCE DECREASED
  - GLOMERULAR FILTRATION RATE DECREASED
  - SERUM CREATININE INCREASED
  - RENAL IMPAIRMENT
  - RENAL FAILURE
  - RENAL FAILURE ACUTE
- Confirmation of eGFR decreases from baseline require that two consecutive measures at least 3 days apart exhibit the decrease.

The null hypothesis  $H_0$  will be rejected in favor of  $H_1$  if there is evidence at the 5% significance level using a 2-sided test.

$H_0$ : There is no statistically significant difference in renal response between voclosporin and placebo at Week 52

$H_1$ : There is a statistically significant difference in renal response between voclosporin and placebo at Week 52.

